## **SECONDARY OUTCOMES AND OTHER MEASURES (RQ-6, PC-3, IR-4)**

**Demographics, health literacy, health status, social support, and media exposure** will be assessed with items we have used in prior studies. Items will assess age, gender, marital/partnered status, number of persons living in the household, ethnicity, race, ethnic origin, education, employment, income, and insurance status. Additional items will assess health literacy, health status, comorbid conditions, and social support for having a colonoscopy. These items have been used for descriptive reporting in our previous research without interpretation or scoring difficulties. In the proposed study, questions about media exposure will assess previous exposure to information about CRC and colon testing.

**Colonoscopy-related procedural anxiety** will be measured using the 6-item short form of the State Anxiety Scale of the State-Trait Anxiety Inventory developed by Spielberger. This scale measures how an individual is feeling right now when thinking about having a colonoscopy. Validity and reliability have been widely reported and this scale has been commonly used in studies of colonoscopy-related anxiety.

**Perceived risk for CRC** will be assessed using two measures that consist of 5 items: a 4-item scale and a single item that assesses comparative age-adjusted risk. The summated risk scale was originally developed for breast cancer and adapted to CRC. Validity and reliability have been extensively tested with diverse population groups. Internal consistency reliability analyses from previous studies yielded Cronbach's alphas ranging from 0.75 to 0.79.

**CRC screening experience and readiness to screen** will be measured separately using 5 categorical items for colonoscopy and 6 categorical items for FIT. These items have been used in our prior studies to stage participants in terms of their readiness to uptake screening behaviors.

**Perceived Benefits** of FIT and colonoscopy will be respectively measured separately using the 3-item and 4-item summated scales used in our prior studies. Cronbach alpha coefficients obtained in preliminary studies were 0.72 for our 3-item benefits of stool testing scale and 0.69 for our 4-item colonoscopy benefits scale.

**Perceived Barriers** to FIT and colonoscopy will be measured by separate summated Likert scales developed and validated by our team and used in previous studies. Barriers to FIT are measured using a 10-item scale; barriers to colonoscopy are measured using a 16-item scale with the same 4-point Likert response options. Cronbach alphas for the FIT barriers scales was 0.82 and for the colonoscopy barriers scale, 0.89.

**Self-efficacy** for FIT and colonoscopy will be measured separately on a 7 item scale for FIT and an 11-item scale for colonoscopy using 4-point Likert response options where 1="not at all sure" to 4="very sure" that I am able to do each of the steps involved in CRC screening. Self-efficacy scales for FIT and colonoscopy had Cronbach alphas of 0.87 and 0.88, respectively, in our previous studies.

**CRC Fear** will be measured using an 8-item scale that assesses participants' emotional reactions to thinking about CRC. This scale was originally developed to assess breast cancer fear and had an internal consistency reliability of .91 in our prior mammography studies. Construct validity has been shown through factor analysis and testing of theoretical relationships. We will adapt the cancer fear scale for CRC by substituting colon cancer for breast cancer.

**Cancer Fatalism** will be measured using Mayo's modification of the Powe Fatalism Inventory, which assesses the degree to which a person equates cancer with death. This scale uses 4-point Likert response options for 11 statements that assess cancer fear, pessimism, predetermination, and inevitability of death. The Cronbach alpha for this scale was 0.86.

**Knowledge of CRC and Screening** will be measured using an 9-item multidimensional scale that has been tested in preliminary studies and found to have content and construct validity. Several aspects of knowledge about CRC and CRC screening tests will be assessed, including risk factors.

**Patient Activation will be measured** using the 13-item short form Patient Activation Measure (PAM) scale developed by Hibbard. It assesses patient knowledge, skill, and confidence for self-management. This scale uses 4-point Likert response options.

**User Experience with the DVD** will be measured using a 15-item scale developed to assess participant's experience with the tailored DVD. The scale will include items to assess cognitive engagement, personal relevance of information, and

esthetic/emotional appeal of the program. Items will be scaled so that higher scores reflect a more positive user experience on all dimensions. Items selected will be based on relevant literature and effective use in our prior studies. We will also include 6 quantitative items to assess the DVD in terms of being helpful, providing new information, and whether or not it would be recommended to others.

**Satisfaction with the Patient Navigator** will be measured using 19 items tailored for study relevancy from the 26-item satisfaction scale used in the national Patient Navigation Research Program. This scale assesses participants' degree of satisfaction with the help received from the navigator using a 3-point response scale where 1=not satisfied and 3=very satisfied. An additional 20 items assess participants' satisfaction with the interpersonal relationship with the navigator using 4-point Likert response options where 1=strongly disagree and 4=strongly agree.

**Trial Participation** feedback will be collected using 4 independent items. Participants will be asked to tell us what they enjoyed, if anything, about being in the study. They will also be asked to tell us what was the hardest part about being in the study. Additionally, participants will be asked if they would recommend the study to others who need a colon test (yes or no response options). Lastly, participants will be asked if they are willing to be contacted in the future about participating in other research studies (yes or no response options).

**C.10. Training of Recruiters and Data Collectors. (PC-2)** Recruiters will be trained by the PI and project manager whereas data collectors will be trained, supervised, and monitored by the Center for Survey Research (CSR) staff in collaboration with the PI. Detailed training manuals for recruiters and data collectors that were developed for our preliminary studies will be modified for the proposed study. Initial training sessions for recruiters and data collectors will include: 1) overview of study objectives and rationale; 2) description of interventions; 3) description of data collection instruments; 4) protection of human subjects, HIPAA and confidentiality issues; 5) cultural sensitivity; 6) roles and responsibilities of project staff members; 7) schedules; 8) documentation and reporting requirements; and 9) quality assurance procedures. Time will be allocated for multiple discussion and question/answer periods. Recruiters will be trained on effective recruitment procedures, including: 1) study recruitment letters, procedures, and telephone scripts; 2) handling problems or questions during telephone recruitment; 3) use of the REDCap tracking database to log recruitment and other study procedures; and 4) recruitment monitoring and quality assurance procedures. Training will include demonstrations of effective recruitment calls. Following demonstrations and practice sessions, recruiters will role-play and receive feedback until they have reached 100% compliance with guidelines for recruitment integrity.

Data collectors selected from CSR for this study will be experienced interviewers. Prior to the study-specific training described below, CSR data collectors will have completed a rigorous 9-hour telephone interviewing training course, with four hours spent in hands-on practical experience in which the trainee-to-supervisor ratio is 5:1. This training course covers: 1) the interviewer's role in survey research; 2) standardized interviewing techniques; 3) administration of survey introductions and refusal aversion techniques; 4) use of computerized sample management and data collection systems; 5) protection of human subjects and sensitive information; and 6) daily case management. Comprehension of concepts and techniques and skill in their execution are assessed through a battery of tests at appropriate intervals in the training course; trainees do not matriculate to the next phase until all prior phases are mastered. Additionally, CSR data collectors will be trained on: 1) specific interviews to be conducted for each wave of data collection; 2) handling problems or questions during data collection; and 3) data monitoring and quality assurance procedures. Training will include demonstrations of effective data collection interviews using the computer-assisted telephone interview software (CATI). Following demonstrations and practice sessions, data collectors will role-play and receive feedback until they have reached 100% compliance with guidelines for data collection integrity.

**C.11. Quality Assurance of Recruitment and Data Collection. (PC-2)** Job performance of data collectors will be closely monitored by the project manager and the IU Center for Survey Research (CSR) supervisors to ensure their adherence to the study protocol. Telephone interviewing stations at the CSR allow supervisors to listen to interviews and view data collectors' computer screens remotely in real-time without the knowledge of the interviewers. All data collectors will be monitored regularly, with a goal of once during every shift. One monitoring session will include listening to at least 20 interview questions. The project manager will routinely listen to randomly recorded recruitment calls to ensure

adherence to the recruitment script and handling of refusals. Ten percent of all interviews and recruitment calls will be monitored for quality assurance purposes. Feedback will be provided after monitoring sessions to correct any performance weaknesses.

**C.12. Sample Size, Power Analyses (RQ-2, RQ-4, IR-3).** The revised sample size estimate of 115 per group for analyses is based on ensuring adequate power for Aim 1 (see Table 4). The main objective is to compare the 12-month CRC screening rates with any test among the three groups, so the binary outcome of any CRC screening test completion at 12 months as documented in the electronic medical record has driven calculation of our sample size. For Aim 1, we will first test whether there is any overall group difference in CRC screening completion rates using a chi-square test at 5% significance level. If a significant difference is observed, pairwise comparisons will be conducted at  $\alpha=1.7\%$  (5%/3 pairwise tests) to account for multiple testing. Expected CRC screening rates, based on prior studies demonstrating the effects of computer-tailored and PN interventions, are shown in Tables 1 and 2, respectively. We have revised our DVD only effect calculations from the original estimate of 15.5% to 20% for this group. We originally proposed a DVD only effect size of 15.5% based upon the average effect size of studies listed in Table 1. This 15.5% estimate assumed that the lowest rate observed in the DVD only group might be near 20% ([name], 2015) and lowered that rate even further to 15.5% to be more conservative, as statisticians typically assume very conservative effects when doing power calculations. However, by assuming a value closer to, but still less than the lowest rate observed in the literature for a comparable population (which was 22% seen in [name], 2015 per Table 1), the samples sizes can be reduced to 115 per group for Aim 1. This sample size will afford at least 80% power for all three comparisons per Table 4 below. To allow for an approximate 25% attrition which the project is experiencing as of May 31, 2019 and still have 115 per group for analyses, a total sample size of 450 enrolled subjects is required.

**Table 4. Revising the expected rate in the DVD group to 20% (still smaller than the smallest rate for a tailored intervention in Table 1)**

Comparison	Rates	Sample Size for Groups	Power
PN+DVD vs DVD only	44% vs 20%	115 vs 115	92%
PN+DVD vs Usual Care	44% vs 5%	115 vs 115	99%
DVD only vs Usual Care	20% vs 5%	115 vs 115	80%

Several studies have shown that patient navigation is an effective method to increase CRC screening rates especially in minority groups with effect sizes shown in Table 2 (average of 33.7). We conservatively estimated a 44% (less than 33.7 + 20 = 54%) effect size for the PN + DVD since we will enroll patients who have previously canceled a screening colonoscopy appointment. For usual care, we used the estimate from [name], 2015 in Table 1 as it is most similar to the proposed study. See Table 5 below for summary. At 12 months, 115 in each group will yield at least 80% power for detecting the pair-wise differences (44% v. 20% v. 5%) in completion rates among the three groups using pair-wise chi-square tests or bivariate logistic regression models and a two-sided  $\alpha=.017$  level. Back-calculation, assuming an attrition rate that is approximately 25% from the sample size needed at 12 months, it requires that we approach 600 eligible subjects to enroll 450 (75% participation rate) and randomly assign them to the three intervention groups (150 per

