**C. Study Design and Approach. (RQ-2, RQ-3, RQ-4, RQ-5, RQ-6)**

We will use a three-group randomized trial design to compare the effectiveness of two theory-based interventions to promote completion of CRC screening among individuals at average risk for CRC and, for those who complete colonoscopy, high quality bowel preparation. We will enroll an ethnically diverse group of 450 men and women who canceled, or did not attend, their colonoscopy appointment and randomize them to receive: 1) a tailored DVD intervention; 2) the tailored DVD *plus* a patient navigator intervention; or 3) usual care. The aims of this study are to:

**1. Compare the effectiveness of two interventions designed to promote CRC screening among people at average risk for CRC - a tailored DVD versus the tailored DVD *plus* telephone-based patient navigation - to each other and to usual care.**

Hypothesis 1.1: Participants who receive the tailored DVD *plus* telephone-based patient navigation intervention will have higher rates of colorectal cancer screening with fecal immunochemical test (FIT), colonoscopy, or either screening test compared to those who receive the tailored DVD alone.

Hypothesis 1.2: Participants who receive either intervention will have higher rates of colorectal cancer screening with fecal immunochemical tests (FIT), colonoscopy, or either screening test than those who receive usual care.

[figure not shown]
Hypothesis 1.3: Participants who receive either intervention who complete colonoscopy will have: 1) better quality of bowel preparation; 2) less anxiety about the procedure; and 3) greater satisfaction with the colonoscopy experience than those who receive usual care.

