**C.8. Data Collection. (RQ-6, PC-2, PC-3)** Trained data collectors/interviewers who are employed by the Indiana University Center for Survey Research (CSR) will collect data via structured telephone interviews. Interviews will be conducted at baseline (T1), at 6 months post-baseline (T2), and at 9 months post-baseline (T3). If unable to reach participants when a phone interview is due, we will mail a letter to them requesting that they contact the CSR data collection team so that the interview may be completed. Reminder letters will be mailed to participants about 1 month before the T2 and T3 interviews are due. Process interviews will be conducted with participants assigned to the DVD intervention group approximately two weeks after mailing of the DVD. The baseline interview includes a question to confirm age eligibility and assesses the following: demographics, health literacy, health status, patient activation, CRC knowledge, CRC fear, cancer fatalism, colonoscopy-related procedural anxiety, social support, and media exposure. For both colonoscopy and FIT, the baseline interview asks questions about participants' experience with each test and readiness to screen by each test. Health beliefs for perceived CRC risk and colonoscopy and FIT perceived benefits, perceived barriers, and perceived self-efficacy are also collected. At completion of the baseline interview, participants will be randomized. People assigned to DVD or DVD + PN intervention groups will be told they will receive a DVD or instructions to access the website to view the program (based on their preference). Those in the tailored DVD + PN group will also be told they also will receive a phone call from the nurse navigator in about a week.

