The DVD process interview will assess receipt of, viewing of, and satisfaction with the DVD and will be done approximately 2 weeks post-mailing of the DVD. Receipt, experience and satisfaction with the PN intervention, for those randomized to the DVD+PN group, will be assessed as part of the 6 month interview (T2). The 6 month interview will also assess changes in knowledge, patient activation, CRC fear, cancer fatalism, and colonoscopy-related procedural anxiety. Health beliefs for colonoscopy and FIT will be assessed as will self-reported CRC screening intention, uptake and satisfaction with the screening experience (for those who completed screening). At 9 months, we will assess self-reported CRC screening intention, uptake and satisfaction with the screening experience (for those who completed screening since T2). Participants will receive a \$50 gift card for the baseline interview, a \$50 gift card for the 6 month interview and a \$50 gift for completing the 9 month interview; a total of \$150 for participants who complete all three interviews. Participants who complete the additional DVD process interview will receive another \$50 gift card for a total of \$200 in gift cards. By using gift cards with an appealing dollar amount over the 9 month data collection period, we hope to incentivize participants to remain in the study. Additional retention strategies which we will use include mailing

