**Table 3: Data Collection Timeline**

Measures	Baseline Interview (T1)	Process Interview (2 weeks after mailing DVD)	Follow-up Interview at 6 months post-baseline (T2)	Final Interview at 9 months post-baseline (T3)	12 months post-baseline (Final medical record review)
Demographics, social support, media exposure	X				
Health literacy, health status to include co-morbidities	X				
CRC screening experience and readiness to screen, patient activation, health beliefs (perceived CRC risk, benefits of screening, barriers to screening, self-efficacy for screening), CRC fear, cancer fatalism	X		X		
Colonoscopy-related procedural anxiety	X		X	X	
CRC and screening knowledge	X		X		
Receipt, viewing and satisfaction with the DVD		X			
Receipt, experience & satisfaction with the PN			X		
Self-report of CRC screening intention and completion			X	X	
Satisfaction with the screening experience			X	X	
Trial participation feedback				X	
Medical record review: CRC screening test completion, quality of bowel preparation			X	X	X

**C.9. Measures.** The primary study outcomes of CRC screening completion with any test (FIT or colonoscopy), and quality of bowel preparation (for those who complete colonoscopy), colonoscopy-related procedural anxiety and satisfaction with the CRC screening experience are described in this section. Secondary outcomes of the interventions include changes in knowledge and health belief variables (perceived risk, benefits, barriers, and self-efficacy). Other measures include patient activation, CRC fear, cancer fatalism, and satisfaction with the interventions. Measures have been extensively tested and refined in preliminary studies, and are described in more detail elsewhere.

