For Aim 1, we will test the primary hypothesis related to comparing intervention effects among the three randomized groups (H1.1: PN+DVD vs. DVD only and H1.2: PN+DVD vs. usual care and DVD only vs. usual care) using the outcome of completion of CRC screening using any test at 12 months post-baseline. In addition, quality of bowel preparation, procedural anxiety, and satisfaction with the screening experience will be examined as outcomes. As an initial assessment of CRC screening completion at 12 months, we will use a chi-square test for a 3 x 2 (group by screening completion) contingency table to test whether completion rates differ across groups. If the  $p$ -value for the overall test is significant at the .05 level, pair-wise 2 x 2 tests will be conducted at the  $.05/3 = .017$  level. However, the primary analyses for Aim 1 will involve fitting multivariable logistic regression models of the primary outcome of 12-month CRC screening test completion (yes/no). Independent variables will be group assignment and continuous and categorical individual characteristics. These models will also allow us to investigate intervention effects on CRC screening test completion while adjusting for potential confounders. Group assignment will be coded using dummy variables with usual care as the reference category. For H1.3, quality of bowel preparation will be analyzed for those participants who complete colonoscopy with proportional-odds ordinal logistic regression using an ordinal dependent variable ( $1 = \text{excellent}$ ,  $2 = \text{good}$ ,  $3 = \text{fair}$ ,  $4 = \text{poor}$ ,  $5 = \text{inadequate}$ ). If some outcome categories are sparse, the outcome will be dichotomized into adequate

(*excellent or good*) versus inadequate (*fair, poor, or inadequate*). The outcomes of anxiety and satisfaction are continuous outcomes and will be modeled with linear regression.

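### H1.3 compares anxiety in colonoscopy completers, but no post-randomisation score is tied to the procedure date, so before- and after-procedure scores are mixed in a small subset selected after randomisation

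*Combined protocol and SAP*

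**What the plan says.** All references are to the combined protocol and SAP.

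- **Hypothesis (section C, H1.3).** "Participants who receive either intervention who complete colonoscopy will have: 1) better quality of bowel preparation; 2) less anxiety about the procedure". The comparator is usual care.
- **Instrument (C.9).** A six-item state anxiety short form: "This scale measures how an individual is feeling right now when thinking about having a colonoscopy". The opening of C.9 lists this anxiety among the primary outcomes, but the scale is described under the secondary-outcomes heading.
- **Timing (C.8 and Table 3).** Baseline comes before randomisation. For follow-up, C.8 states: "The 6 month interview will also assess changes in knowledge, patient activation, CRC fear, cancer fatalism, and colonoscopy-related procedural anxiety". For the last interview it lists other items: "At 9 months, we will assess self-reported CRC screening intention, uptake and satisfaction with the screening experience". Anxiety is absent from that list, whereas Table 3 marks it at baseline, 6 and 9 months.
- **Other contacts.** The process interview two weeks after mailing covers only the DVD (C.8). The navigator's call shortly before an appointment exists in one arm and lists no anxiety scale (C.4.b).
- **Analysis (C.13).** "The outcomes of anxiety and satisfaction are continuous outcomes and will be modeled with linear regression". No time point, baseline adjustment or rule for scores before versus after the procedure is given.
- **Power (C.12).** 99% for continuous Aim 1 outcomes at 0.50 SD, with 115 per group.

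**The concern.** Being asked how one feels about having a colonoscopy means something different before the test than after it. The interviews run on time from baseline and colonoscopies occur whenever they occur, so a completer's 6-month score may fall on either side of the procedure. The interventions are meant to bring completion about, so the share of scores taken afterwards may differ by arm. A lower mean in an intervention arm could then reflect, in part, more people having the test behind them, yet be reported as less anxiety about the procedure.

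Two further problems come with the completer restriction. Completion is itself an outcome the interventions should change, so completers in different arms need not be comparable. There will also be very few of them under usual care, so the power statement, which counts everyone analysed, does not describe this comparison.

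**Working it through.** **1. Which scores exist, by date of colonoscopy.** Completion is counted to 12 months (C.13). Taking Table 3 at face value for the 9-month score:

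| Colonoscopy at | 6-month score | 9-month score |
|---|---|---|
| before 6 months | after procedure | after procedure |
| 6 to 9 months | before | after |
| 9 to 12 months | before | before |

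The first row has no score that is both post-randomisation and pre-procedure. This follows from the schedule and needs no assumption.

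**2. How many fall in each row.** The documents give no dates. Five assumed patterns within the 12-month window show the range. For the exponential patterns, the share before month x is F(x)/F(12), with F(x) = 1 − 2^(−x/m) and m the median before truncation at 12 months.

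| Assumed timing | Before 6 months | Before 9 months |
|---|---|---|
| Uniform, 0–12 | 6/12 = 50% | 9/12 = 75% |
| Exponential, m = 3 | 0.750/0.9375 = 80% | 0.875/0.9375 = 93% |
| Exponential, m = 6 | 0.500/0.750 = 67% | 0.646/0.750 = 86% |
| Uniform, 3–12 | 3/9 = 33% | 6/9 = 67% |
| Uniform, 5–12 | 1/7 = 14% | 4/7 = 57% |

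The after-procedure share is 14–80% at 6 months and 57–93% at 9 months.

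**3. The plan's power figure.** At 0.50 SD, two-sided 0.05, normal approximation:

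- Both interventions pooled against usual care, 230 vs 115: SE = √(1/230 + 1/115) = 0.114; 0.50/0.114 = 4.38; power = Φ(4.38 − 1.96) = 0.992. This reproduces 99%.
- 115 vs 115: 0.967 (0.920 at the pairwise level of 0.017).

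C.12 does not name the contrast, but its figure counts all 115 analysed per group.

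**4. The same calculation in completers.** The planning rates for any test are 44%, 20% and 5% (C.12). They are upper bounds for colonoscopy because FIT also counts.

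- 115 × 0.44 = 50.6, 115 × 0.20 = 23.0 and 115 × 0.05 = 5.75: about 51, 23 and 6.
- Either intervention vs usual care, 74 vs 6: SE = √(1/74 + 1/6) = 0.42 SD; 0.50/0.4245 = 1.18; power 0.217 by normal approximation and 0.214 by noncentral t.
- DVD plus navigation vs usual care, 51 vs 6: 0.21. DVD alone vs usual care, 23 vs 6: 0.18.
- If all 150 per group were interviewed (66, 30, 8), either vs usual care: 0.27.

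**5. Size of a timing artefact, for illustration only.** Assume 80% of navigated completers and 50% of usual-care completers have had the procedure by 6 months, and that having had it lowers the score by 0.3–0.5 SD. Then (0.80 − 0.50) × 0.3 to 0.5 = 0.09–0.15 SD with no true effect. With equal shares the artefact is zero. If scores rise after the procedure, it reverses sign.

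**6. Does comparing everyone at 6 months remove it?** No. On the same assumptions the post-procedure shares are 0.44 × 0.80 = 0.352 and 0.05 × 0.50 = 0.025. The difference of 0.327 times 0.3–0.5 SD is 0.10–0.16 SD.

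**The case against.** Three stronger readings are tempting, and the documents do not support them.

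- *The hypothesis is not tested.* A linear regression is planned, and H1.3 never says the anxiety must precede the procedure. It sits beside satisfaction with the colonoscopy, which can only be measured afterwards.
- *Most completers are scored after the procedure.* The navigator's first call about two weeks after mailing (C.4.b) and the usual 4–5 weeks from referral to appointment (C.4) make early completion plausible. But participants have already missed an appointment, calls are rescheduled if the DVD is unviewed, and navigation continues as long as needed. At 6 months the share depends on dates the plan does not give.
- *The bias is 0.09–0.15 SD.* Every input to that figure is assumed. Even at face value it is small against a standard error of about 0.42 SD: the two-sided 5% error rate would rise only to about 5.5–6.4%.

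It can also be said that C.13 states the completer restriction for bowel preparation and does not repeat it for anxiety, so an all-participant analysis may be intended; that anxiety does not drive the sample size; and that baseline anxiety, record dates and sensitivity analyses as needed are already planned. The ambiguity is real. But H1.3 names completers, and the generic sensitivity clause sets no time point or timing rule. If everyone is to be analysed, H1.3 must be reworded. If only completers are, the 99% does not apply.

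The objection that a 6-month comparison of all participants still contains after-procedure scores is correct (step 6), and the conclusion must say so.

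**Conclusion.** The point holds in this form. The schedule alone establishes that anyone completing before 6 months has no post-randomisation, pre-procedure anxiety score. A regression restricted to completers, as H1.3 is worded, would mix before and after scores with no stated rule, in a subset formed after randomisation. At the plan's own rates that subset is at most about 74 vs 6, with power near 0.21 at 0.50 SD. This rests on the 44/20/5% rates, 115 analysed per arm and two-sided 0.05; fewer colonoscopies would lower it further.

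The share of completers scored after the procedure, any imbalance in that share between arms, and the size and direction of any bias are unknown. The primary screening analysis is unaffected. The point deserves action because C.9 places anxiety among the primary outcomes and the correction is cheap.

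**What to change.** 1. Define the anxiety analysis as a comparison of 6-month scores by randomised arm in all interviewed participants, adjusted for the baseline anxiety score.
2. Word the conclusion as anxiety about colonoscopy at 6 months, and state that part of any difference may reflect having already had the test.
3. Among completers, use the colonoscopy date from the medical record to label each score as before or after the procedure. Report these descriptively, and make no claim about pre-procedure anxiety from after-procedure scores.
4. Reword H1.3 to match, and reconcile C.8 with Table 3 on whether anxiety is measured at 9 months.

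The cost is wording in the hypothesis and analysis plan. The 6-month scores and colonoscopy dates are already to be collected. With about 25% attrition, 150 × 0.75 = 112.5 per arm would be interviewed, close to the 115 behind the stated power. The completers-only anxiety claim is given up. The revised comparison is randomised, apart from missed interviews, but it does not isolate anxiety before the procedure.
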